6.8.2 Imputation Rules for Incomplete Dates

For AEs, a missing or incomplete onset date will be imputed according to the following conventions.

If an onset date is missing, the imputed onset date will be the date of first dose of study drug.

If only the year is known for the AE onset date, the imputed onset date will be the latest of the following non-missing dates:

- Date of first dose of study drug
- January 1 of the year of AE onset date

If only the month and year is known for the onset date, set the surrogate onset date to the first day of that month and then apply the following rules.

- If the month and year of the onset date is prior to the month and year of the first dose of study drug, then the surrogate onset date will be the imputed onset date.
- If the month and year of the onset date is on or after the month and year of the first dose of study drug, then the imputed onset date will be the latest of the following non-missing dates:
- Date of first dose of study drug
- Surrogate onset date
- If the imputed onset date is after the AE end date, the imputed onset date will be the same as the AE end date.

For duration of disease of primary diagnosis, a missing or incomplete diagnosis date will be imputed according to the following conventions.

If a diagnosis date is missing, the diagnosis date will not be imputed. The duration of disease in baseline analysis will be treated as missing data.

If only the year is known for the diagnosis date, the imputed diagnosis date will be January 1 of the year of the diagnosis date.

If only the month and year is known for the diagnosis date, set the imputed diagnosis date will be the first day of that month.

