9.5 Additional Conventions

If the start and stop dates of AEs and concomitant medications are incomplete, imputed dates will be used to determine whether an AE is/is not treatment emergent or to allocate a concomitant medication to the study period it was taken.

Refer to the SAPs for details of the definition for analysis windows to be used for analyses by visit.

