5.4 Primary Safety Endpoints

5.4.1 Treatment Emergent Adverse Events (TEAEs)

AE collection begins after the ICF has been signed and continues until the follow up visit or 28 days after the final IP administration or when the participant is determined to be a screen failure. A TEAE is defined as an AE observed after starting administration of the IP to 28 days after the last dose of IP for double-blind treatment period of the study or moving to the OLE part, whichever comes first.

An IP-related TEAE is defined as any TEAE with a causal relationship of "yes" by the investigator.

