5.2 Safety Endpoints

5.2.1 Treatment Emergent Adverse Events (TEAEs)

AE collection begins after the ICF has been signed and continues until the follow up visit or 28 days after the final IP administration or when the participant is determined to be a screen failure. A TEAE is defined as an AE observed after starting administration of the ASP0367 to 28 days after the last dose of ASP0367.

An IP-related TEAE is defined as any TEAE with a causal relationship of "yes" by the investigator.

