6.2 Study Population

6.2.1 Disposition of Participants

The following participant data will be presented:

Analysis population: All participants who complete double blind part, Analysis group: ASP0367 any dose group, Placebo to ASP0367 group and Total

- Number and percentage of participants who were administered at least one dose of study drug during the OLE part,
- Number and percentage of participants who completed and those who discontinued the treatment during the OLE part, by primary reason for treatment discontinuation,
- Number and percentage of participants who completed and those who discontinued the follow-up period, by primary reason for follow-up discontinuation.

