6.3 Study Drugs Exposure and Compliance

Analysis population: SAF, Analysis group: ASP0367 any dose group or Placebo to ASP0367 group

• The duration of ASP0367 exposure for each participant will be summarized by descriptive statistics and frequency tabulations. The following categories of the duration of exposure (days) will be defined:

```
< 29 (4 weeks)

>= 29 (4 weeks) to < 85 (12 weeks)

>= 85 (12 weeks) to < 169 (24 weeks)

>= 169 (24 weeks) to < 253 (36 weeks)

>= 253 (36 weeks) to < 365 (52 weeks)

>= 365 (52 weeks) to < 449 (64 weeks)

>=449 (64 weeks) to <533 (76 weeks)

>=533 (76 weeks)
```

The duration of ASP0367 exposure will be calculated as follows: {"Date of Last Study Drug Taken" – "Date of First ASP0367 Taken*"} + 1.

Date of Last Study Drug Taken is defined as the latest date of ["Date of Last Study Drug Taken (Phase 2 Treatment Period)", "Date of Last Study Drug Taken (Dose selection Period)", or "Date of Last Study Drug Taken (Open-Label Extension Part)"].

- *: For participants received ASP0367 on double blind part, "Date of First Study Drug Taken" will be used. For participants received placebo on double blind part, "Date of First Study Drug Taken (Open-Label Extension Part)" will be used.
- The compliance of ASP0367 exposure for each participant will be summarized by descriptive statistics and frequency tabulations. The following categories of the study drug compliance (%) will be defined:

```
    < 50

    >= 50 to < 75

    >= 75 to < 90

    >= 90
    Unknown
```

The compliance of study drug exposure for ASP0367 any dose group will be calculated as follows:

Total number of dispensed tablets of ASP0367 - Total number of returned tablets of ASP0367 ×100

The number of tablets of ASP0367 to be taken

The number of tablets to be taken is defined as follows;

[{"Date of Last Study Drug Taken" – "Date of First Study Drug Taken"} + 1] x the number of tablets per day.

The compliance of study drug exposure for Placebo to ASP0367 arm will be calculated as follows:

Total number of dispensed tablets in OLE part - Total number of returned tablets in OLE part

The number of tablets to be taken in OLE part

The number of tablets to be taken in OLE part is defined as follows;

["Date of Last Study Drug Taken (Open-Label Extension Part)" – "Date of First Study Drug Taken (Open-Label Extension Part)" + 1] x the number of tablets per day.

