6.5.1 Adverse Events

AEs will be coded using the MedDRA.

An overview table will include the following:

- Number of TEAEs,
- Number and percentage of participants with TEAEs,
- Number of drug related TEAEs,
- Number and percentage of participants with drug related TEAEs,
- Number of serious TEAEs,
- Number and percentage of participants with serious TEAEs,
- Number of serious drug related TEAEs,
- Number and percentage of participants with serious drug related TEAEs,
- Number of TEAEs leading to death,
- Number and percentage of participants with TEAEs leading to death,
- Number of drug related TEAEs leading to death,
- Number and percentage of participants with drug related TEAEs leading to death,
- Number of TEAEs leading to withdrawal of study drug,
- Number and percentage of participants with TEAEs leading to withdrawal of study drug,
- Number of drug related TEAEs leading to withdrawal of study drug,
- Number and percentage of participants with drug related TEAEs leading to withdrawal of study drug, and

• Number of deaths.

The number and percentage of participants with TEAEs, as classified by SOC, and PT will be summarized by analysis group. Summaries will be provided for the following:

- TEAEs.
- drug related TEAEs,
- serious TEAEs,
- drug related serious TEAEs,
- TEAEs leading to withdrawal of study drug,
- drug related TEAEs leading to withdrawal of study drug,
- TEAEs excluding Serious AEs that equal to or exceed a threshold of 5.0% in any analysis group.

The number of TEAEs and the number and percentage of participants with TEAEs, as classified by SOC and PT will be summarized by severity and by relationship to study drug. In the participant count, if a participant has multiple TEAEs with the same SOC or PT, but with differing severity or relationship, then the participant will be counted once with the worst severity and highest degree of relationship. If severity or relationship is missing for all episodes of the event, the participant will be counted under missing severity or relationship.

The following AESIs are defined:

- Cardiac tissue injury defined by cTnI above ULN or if the cTnT is above ULN or baseline if the participant's baseline value was above ULN and a TEAE as pre-defined by a MedDRA search strategy for elevated troponin.

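### 76-week SAP 6.8.2 dates incomplete AE onsets from first study drug, so some events that began on ASP0367 in placebo switchers can drop out of its TEAE tables (minor)

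*SAP*

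**What the plan says.** The SAP file holds two plans, both dated 9 July 2024. One covers the 52-week double-blind part; the other covers the double-blind part plus the OLE, up to 76 weeks.

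- **Role of imputed dates.** Protocol 9.5 says that "imputed dates will be used to determine whether an AE is/is not treatment emergent".
- **Imputation rule, 76-week SAP 6.8.2.** For a fully missing onset: "If an onset date is missing, the imputed onset date will be the date of first dose of study drug". A year-only onset becomes the later of that first dose and 1 January of the year. A month-and-year onset becomes the first of the month, or the first dose if that is later and the month is not before the first-dose month. The 52-week SAP 6.8.2 has the same rule.
- **TEAE, 76-week SAP 5.2.1.** "A TEAE is defined as an AE observed after starting administration of the ASP0367 to 28 days after the last dose of ASP0367". The Introduction adds that placebo-to-ASP0367 switchers are analysed in the OLE part only.
- **TEAE, 52-week SAP 5.4.1.** The window opens at the first IP dose, placebo included, and closes 28 days after the "last dose of IP for double-blind treatment period of the study or moving to the OLE part, whichever comes first".
- **First-dose dates, 76-week SAP 6.3.** For placebo participants, ASP0367 exposure starts at a separate field that begins "Date of First Study Drug Taken (Open-Label Extension Part".
- **Another use of the term, 76-week SAP 6.2.1.** Disposition counts those given "at least one dose of study drug during the OLE part".
- **Events of special interest, 76-week SAP 6.5.1.** The troponin criterion needs the laboratory finding and "a TEAE as pre-defined by a MedDRA search strategy for elevated troponin".

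**The concern.** For a switcher, first study drug and first ASP0367 are about a year apart. The imputation rule uses the first and the 76-week TEAE definition uses the second, so an incomplete date can move an event that began on ASP0367 back into the placebo period.

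This looks like an oversight. The rule suits the 52-week SAP, where first study drug is the correct start. Elsewhere the 76-week SAP adapts to switchers: exposure (6.3), walking-aid baseline (6.2.3), laboratory denominators and the CK isoenzyme baseline (6.5.2), body weight (6.5.5.1) and visit baseline (6.8.1). The AE rule in 6.8.2 has no such adaptation.

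Safety is the only analysis in the 76-week SAP. On the natural reading the error runs one way: events on ASP0367 are missed in the switcher group and may be credited to placebo in the companion tables.

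**Working it through.** The documents give no figure to reproduce. The check applies the stated rules to assumed dates.

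**Notation.** P is the first placebo dose and A the first ASP0367 (OLE) dose.

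**Inputs.** The 52-week double-blind and 24-week OLE periods come from the 76-week SAP Introduction. Assumptions: A falls on each of the 365 days of 2023 with equal weight; P = A − 364 days; true OLE onset is uniform over 168 days; the OLE starts within 28 days of the last double-blind dose.

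**Reading 1: study drug includes placebo, so the anchor is P.** The 365 × 168 = 61,320 pairs of switch date and onset date give:

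- *Fully missing.* Imputed to P, always before A: 61,320/61,320 = 100%.
- *Year-only.* Imputed to 1 January of the switch year (or P if later) when the onset is in that year; wrong unless A is 1 January. With A on day d of the year, the count is the sum over d = 2 to 365 of min(168, 366 − d). Days 2–198 give 197 × 168 = 33,096 and days 199–365 give 167 × 168/2 = 14,028, total 47,124. 47,124/61,320 = 76.8%, range 0–100% by switch date.
- *Month-and-year.* Imputed to the first of the switch month when the onset is in that month; wrong unless A is the first. A month of L days contributes L(L − 1)/2 pairs: 7 × 465 + 4 × 435 + 378 = 5,373. 5,373/61,320 = 8.8%, range 0 to 30/168 = 17.9%.

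With onset spread over 196 days, the shares are 100%, 73.0% and 7.5%. Every misplaced date satisfies P ≤ imputed date < A, so it falls inside the 52-week placebo TEAE window.

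**Example.** P = 15 March 2022, A = 14 March 2023. A missing onset becomes 15 March 2022; 2023 becomes 1 January 2023; March 2023 becomes 1 March 2023. All three precede A. April 2023 becomes 1 April 2023, which is correctly in the OLE.

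**Reading 2: study drug means ASP0367, so the anchor is A.** No OLE-onset event is misplaced. But a year-only placebo-onset event from a calendar year before the switch is moved to A, against its known year. Of the 365 × 364 = 132,860 placebo-onset pairs (events ongoing at A), all year-only onsets count as ASP0367 TEAEs, and half (50.0%) are known to come from the earlier year.

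**Proposed rule (see the fix).** OLE-onset events misplaced: 0% for each pattern. Placebo-onset events not ended before A that would count as ASP0367 TEAEs:

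- fully missing: 100%;
- year-only: (364 × 365/2)/132,860 = 66,430/132,860 = 50.0%;
- month-and-year: 5,373/132,860 = 4.0%.

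**The case against.** **The wording can be read the other way.** Section 6.8.2 does not cite the 6.3 first-dose field, and most of the 76-week SAP starts the switchers' clock at ASP0367. This stands in part: reading 1 is natural but not explicit. Reading 2 does not rescue the rule, because it overrides a known year.

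**The worst patterns should be rare.** The visits in 76-week SAP 6.8.1 are at most four weeks apart, and protocol 7.3.1 requires SAEs to be reported within 24 hours. Month-only gaps are the more plausible ones, and there the share is about 9%. This stands, and it is a main reason the point is minor.

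**The fix trades one error for another.** With equal AE rates in both periods, a fully missing onset with no known end date is more likely to have begun on placebo: 364/(364 + 168) = 364/532 = 68%. The arithmetic is right. But 6.8.2 already assigns an unknown onset to the first dose, so that the event counts as treatment-emergent. Moving the switchers' anchor to first ASP0367 extends that cautious convention to the drug this SAP evaluates.

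**A stronger claim about the tables.** A reader might infer that the 76-week SAP itself tabulates these events as placebo TEAEs. It cannot: its groups are ASP0367 any dose and Placebo to ASP0367 (6.1, 6.5), with no placebo column. Placebo tabulation arises only through the 52-week SAP.

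**Conclusion.** The mismatch is in the text, and the rule needs repair under either reading. On the natural reading, a switcher's OLE-onset event with one of the three date patterns leaves the 76-week TEAE tables and the special-interest counts that require a TEAE, and would appear as a placebo TEAE in the 52-week tables. There is no error for the year-only or month-only pattern if the switch is on the first day of that year or month. Participants randomised to ASP0367 are not affected.

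The sizes are 100% (fully missing), about 77% (year-only, 0–100%) and about 9% (month-only, 0–18%). They are shares of switchers' OLE-onset events with incomplete dates, under the date assumptions above. The documents do not say how many such events exist, and the effect may be zero. Severity: minor.

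Two further inferences are not supported. The events are not lost from the record: protocol 9.4.3.1 lists all AE data, and laboratory and ECG summaries do not use AE onset dates. Nor does the table of "TEAEs excluding Serious AEs that equal to or exceed a threshold of 5.0% in any analysis group" add weight: that one event can reach the threshold in a small group follows from group size, not from imputation.

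**What to change.** In 76-week SAP 6.8.2, for the Placebo to ASP0367 group only:

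- Impute the onset to the first ASP0367 (OLE) dose when it is fully missing, when only the year is known and it is the switch year, or when only month and year are known and they are those of the switch.
- Keep the current rule for every other pattern, with the first placebo dose named as the anchor.
- State that the AE end-date cap applies to all three patterns; the layout leaves its scope unclear. The cap keeps events that ended on placebo out of the ASP0367 counts.

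In 52-week SAP 6.8.2, use the same imputed date and count an onset on the switch date in the OLE only. If only the 76-week SAP is changed, each moved event would also remain a placebo TEAE in the 52-week tables. List switchers' AEs with imputed onsets.

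The cost is a few SAP and program lines, or a CSR note and one listing if the database is already locked. The price is the over-counting shown above (100%, about 50% and about 4% of placebo-onset events not ended before the switch, by pattern). That is the conservative direction the SAP's own convention already takes, and the listing makes it visible.

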6.8.3 Outliers

All values will be included in the analyses.

7 REVISION AND RATIONALE

Version	Date	Changes	Comment/rationale for change	
1.0	09-JUL-2024	NA	Document finalized	

